#### **Hypothesis 2:**

Those randomized to AHA's Depression Screen, Notify & Treat intervention group will have a favorable incremental cost-effectiveness ratio when compared to No Depression Screen control group and also when compared to the Depression Screen & Notify control group.

For this hypothesis, we will judge the cost effectiveness of AHA Screen, Notify & Treat group compared to the Screen & Notify group, then we will compare the Screen & Notify group to the No Screen group on the basis of incremental cost-effectiveness ratios. The base case analysis will adopt a societal perspective with respect to costs and health benefits. Costs will include all healthcare costs and lost productivity cost related to use of website/staff time for depression screening, and the cost of all possible depression care used (antidepressant cost and therapy cost, including the cost for telephone/webcam use). Costs will be denominated in 2012 dollars and discounted at an annual rate of 3% as per the Panel on Cost-Effectiveness in Health and Medicine. For health benefits, we will convert SF-12 scores to QALYs, using the four (prerandomization, 6, 12, & 18 month) measured values. Incremental cost-effectiveness analyses for comparison of treatment groups will be calculated sequentially using the ratio of the difference in average cost per participant divided by the difference in average QALY gained.

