# **Introduction**

#### **Background and Rationale**

Patients with an acute coronary syndrome (ACS) and comorbid depression have a 2fold higher risk for recurrent ACS and mortality, worse quality of life, and higher costs of care than non-depressed ACS patients. The strength of these observational findings prompted the American Heart Association (AHA) to advise that routine depression screening for ACS patients and referral for depression diagnosis and treatment as indicated occur. Unfortunately, there are no randomized controlled trials (RCT) to inform this large, potentially expensive screening recommendation. And, screening guidelines/advisories in the absence of RCT evidence have recently been extensively criticized (and withdrawn). This poses a serious dilemma for clinicians, health care systems, and for health care policy leaders. An RCT is urgently needed to provide evidence for these different constituents about the costs and benefits of the AHA depression screen and treat algorithm. Two critical gaps in knowledge must be filled to determine if public health would be improved by the AHA strategy for depression screening in post-ACS patients: 1) Does this strategy improve quality-adjusted life years for patients with a recent ACS (primary outcome)? and 2) Is the cost of providing depression screening and any type of depression treatment within the acceptable and typical amounts reimbursed for health care services?

Our **specific aim** is to determine the quality-adjusted life year benefits (primary outcome) and health care costs of following the AHA's advisory for depression screening and then referral for further diagnosis and treatment in post-ACS patients, if elevated depressive symptoms are found. To accomplish this aim, we will randomize patients from four different, geographically diverse health systems to three different groups: 1) to the AHA depression screen, notify, and treat if elevated depressive symptoms are found algorithm (intervention group) or: 2) to receive no depression screening (strong control group) or: 3) to be screened and a primary care provider notified of elevated depressive symptoms (minimally enhanced control group). Health-related quality of life, depressive symptoms, and costs will be obtained from all patients, so that the benefits and the costs of these three different depression screening strategies can be compared.

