# **Objectives/Hypothesis**

The overarching goal of this research is to conduct a state-of-the-art RCT that will rigorously evaluate the benefits and costs of AHA's depression advisory for modern post-ACS patients.

To examine in a randomized controlled trial the benefits and costs of the AHA's advisory for depression screen and treatment of post-ACS patients.

**Hypothesis 1:** Screen, notify, & treat intervention group will gain significantly more quality-adjusted life years (primary outcome) across 18 months when compared to No Depression screen control group, and also when compared to the Depression screen & notify control group.

**Hypothesis 2:** Those randomized to AHA's Depression screen & treat intervention group will have a favorable incremental cost-effectiveness ratio when compared to No Depression screen control and also when compared to the Depression screen & notify control group.

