#### Sample Size

For the primary outcome in Aim 1, we will be making two primary comparisons: Difference in QALYs comparing AHA's Screen, Notify & Treat group vs. Screen & Notify and then separately to No Screen group. For choosing a sample size, we assumed a standard deviation for QALYs in the conservative control group (e.g., no depression screen) of 0.17. Additionally, based on a prior study of management of depression for patients with cancer, we assumed a net improvement in QALYs of 0.155 over 18 months of follow-up for individuals receiving the AHA's screen & treat intervention would be reasonable to expect. We assumed a 0.055 gain in QALYs for all participants not receiving treatment (i.e., those in the No Screen group, the Screen & Notify group and those without depression in the AHA's Screen, Notify & Treat group). An important consideration for this trial is that only 20% of patients randomized to the AHA's Screen, Notify & Treat group will meet criteria for depression and thus will receive the treatment part of intervention. Therefore, assuming an improvement in QALYs of 0.21 (0.055 background improvement + net improvement of 0.155) over the 18-month follow-up period for the 20% of participants with diagnosed depression and a 0.055 improvement in QALYs for the 80% of participants in this randomization group without depression, an overall gain in QALYs of 0.086 over the 18-month follow-up period can be anticipated in

\*\* For blinded coordinator only

\*Only completed if necessary

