2.2 Objectives

The overarching goal of this research is to conduct a state-of-the-art RCT that will rigorously evaluate the benefits and costs of AHA's depression advisory for modern post-ACS patients.

To examine in a randomized controlled trial the benefits and costs of the AHA's advisory for depression screen and treatment of post-ACS patients.

Hypothesis 1: Screen, notify, & treat intervention group will gain significantly more quality-adjusted life years (primary outcome) across 18 months when compared to No Depression screen control group, and also when compared to the Depression screen & notify control group.

Hypothesis 2: Those randomized to AHA's Depression screen & treat intervention group will have a favorable incremental cost-effectiveness ratio when compared to No Depression screen control and also when compared to the Depression screen & notify control group.

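### Hypothesis 2 calls for a cost-effectiveness ratio of Screen, Notify & Treat against No Screen, but the planned analyses do not list it, and the sequence they do list has no dominance rule

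*Protocol*

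**What the plan says.** Hypothesis 2 appears three times with the same two contrasts. In the Protocol's Objectives/Hypothesis section, Treat is to have a "favorable incremental cost-effectiveness ratio when compared to No Depression screen control and also when compared to the Depression screen & notify control group". The Statistical Methods section, under Hypothesis 2, repeats it as a "favorable incremental cost-effectiveness ratio when compared to No Depression Screen control group and also when compared to the Depression Screen & Notify control group". SAP section 2.2 carries it over, again beginning with a "favorable incremental cost-effectiveness ratio when compared to No Depression screen control".

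The method paragraph directly below the hypothesis in the Protocol names two comparisons. In the first, "we will judge the cost effectiveness of AHA Screen, Notify & Treat group compared to the Screen & Notify group"; and "then we will compare the Screen & Notify group to the No Screen group on the basis of incremental cost-effectiveness ratios". It adds: "Incremental cost-effectiveness analyses for comparison of treatment groups will be calculated sequentially", each ratio being the difference in mean cost over the difference in mean QALYs gained.

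The Protocol's Sensitivity Analysis section adds cost scenarios, ratios by health system, Monte Carlo ranges and a payer perspective, but no further contrast between arms. SAP section 8 describes how costs and productivity are measured and priced. It names no ICER contrast and gives no ratio formula. Neither document says what happens if an arm is dominated or extendedly dominated, or if a QALY difference is zero or negative.

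**The concern.** The hypothesis and its method do not match. Hypothesis 2 needs Treat against No Screen and Treat against Screen & Notify. The method supplies the second of these, and Screen & Notify against No Screen in place of the first. Followed as written, the plan does not report one of its two hypothesised ratios, and the comparator left out of the Treat ratios is the arm that the Protocol's Background and Rationale calls the strong control.

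Reading the text as a stepwise analysis of ordered strategies does not settle the matter. Such an analysis first removes arms that cost more for no more benefit (dominance), or that reach their benefit at a worse rate than the next arm (extended dominance), and only then forms ratios between neighbours. Here the pairs are fixed in advance. If Screen & Notify turned out to be dominated, the listed Treat ratio would be measured against an arm that a stepwise analysis would have dropped, and the ratio that mattered would be the unlisted one.

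**Working it through.** **1. Contrasts side by side.**

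| Contrast | In Hypothesis 2 | In the method | Planned QALY difference |
|---|---|---|---|
| Treat vs No Screen | yes | no | 0.086 − 0.055 = 0.031 |
| Treat vs Screen & Notify | yes | yes | 0.086 − 0.055 = 0.031 |
| Screen & Notify vs No Screen | no | yes | 0.055 − 0.055 = 0 |

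**2. Inputs** (Protocol, Sample Size; SAP 5.4). SD of QALYs 0.17, applied here to every arm; 475 analysed per arm; two-sided 5%; 80% power. On the controls the Protocol says: "We assumed a 0.055 gain in QALYs for all participants not receiving treatment", and it counts both the No Screen and the Screen & Notify arms among them. Treat: 0.21 × 0.2 + 0.055 × 0.8 = 0.086.

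**3. The plan's own figure.** n = 2 × (1.960 + 0.842)² × 0.17² / 0.031² gives 473 per arm, against 475 stated; power at 475 is 80.2%. 475 / 0.95 = 500. The inputs are read correctly.

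**4. Stability of each denominator.** SE of a difference = 0.17 × √(2/475) = 0.0110.
- Screen & Notify vs No Screen: expected value 0, 95% range ±1.96 × 0.0110 = ±0.022. Either sign is equally likely, and the observed value falls within ±0.005 QALY with probability 35%.
- Treat vs No Screen: 0.031 / 0.0110 = 2.81 SE above zero, so it is negative with probability 0.25%.

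For illustration only, take a fixed cost difference of $100, which is not in the documents; the results scale in proportion to it. The central 95% of simulated ratios runs from about −$143,000 to +$144,000 per QALY for Screen & Notify vs No Screen, and from about $1,900 to $10,200 for Treat vs No Screen.

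**5. Can the missing ratio be recovered?** Yes. The two listed steps add up: (cost difference Treat − Screen & Notify, plus cost difference Screen & Notify − No Screen) divided by the sum of the two matching QALY differences is the Treat vs No Screen ICER.

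**6. What dominance does to the listed Treat ratio.** Let Treat have extra cost C > 0 and QALY gain d > 0 over No Screen, and let Screen & Notify have extra cost rC and gain fd. Then

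ICER(Treat vs Screen & Notify) / ICER(Treat vs No Screen) = [C(1 − r) / d(1 − f)] / [C / d] = (1 − r)/(1 − f).

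For r between 0 and 1, Screen & Notify is dominated if f ≤ 0 and extendedly dominated if 0 < f < r. In both cases the quotient is below 1, so the listed ratio looks better for Treat than the hypothesised one. If f lies between r and 1, the listed ratio is the higher of the two and is the proper stepwise ratio. Illustrations with assumed values: r = 10%, f = 0 gives 0.90 (10% lower); r = 10%, f = 20% gives 0.90/0.80 = 1.125 (12.5% higher). The documents do not give r, and because the costs cover all health care it could be negative or exceed 1.

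**The case against.** The strongest reply is that little is lost. The missing ratio is named in the hypothesis, the formula is given, and step 5 shows that it follows from the listed steps. The Protocol's Sample Size section and the SAP footnote in section 8 both say that no economic hypotheses needing statistical tests were planned, so no error rate or decision rule hangs on the listed pairs. All of that stands, and it limits the weight of the point. It does not remove the mismatch: three ratios can be formed from three arms, and the set that the plan commits to differs from the set that it hypothesises.

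A reader might infer that Screen & Notify versus No Screen is itself a mistake. The documents do not support that. Protocol Background and Rationale, Trial Design, and SAP section 1 all aim to compare the benefits and costs of three strategies, and this ratio serves that aim.

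A reader might also infer that the ratio is bound to be undefined. That goes too far. The equal 0.055 gains are a simplification made to size the QALY test; they do not predict the observed difference. The Protocol also plans 95% intervals for cost and effectiveness, so a QALY difference near zero would be visible. What stands is that on the trial's own assumptions the ratio can be unstable or change sign, and no rule covers that case.

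Finally, it is fair to say that sequential calculation may imply the usual removal of dominated arms. Neither document says so, and pairs fixed in advance point the other way.

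**Conclusion.** The point holds as a mismatch between a stated hypothesis and its planned analysis. One of the two ICERs in Hypothesis 2 is not listed, the SAP does not supply it, and the sequence given in its place has no dominance rule. The comparison of denominators (0 against 0.031, SE 0.011) rests on the sample-size assumptions: an SD of 0.17 in each arm, 475 per arm and equal gains in the controls.

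It might be tempting to conclude that the plan flatters Treat by some percentage. The documents do not support a figure. They give no costs, so neither the size nor the direction of any distortion is known; the percentages in the working only restate assumed inputs with costs held fixed. Nor does it follow that Screen & Notify should be dropped as a comparator for Treat: Hypothesis 2 requires that ratio whether or not the arm is dominated.

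No data are lost. The analysis is secondary and untested, and the primary QALY analysis and sample size are untouched. The text should still be corrected, because cost-effectiveness is one of the trial's two stated hypotheses.

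**What to change.** In the Protocol's Hypothesis 2 method, and in a short new SAP section on cost-effectiveness:

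- Name Treat vs No Screen and Treat vs Screen & Notify as the two Hypothesis 2 ICERs, both reported whatever the ordering of the arms.
- Keep Screen & Notify vs No Screen as part of a sequential table. Order the arms by mean cost and remove dominated and extendedly dominated arms before forming ratios.
- Where a QALY difference is near zero or negative, report incremental net monetary benefit over a threshold range stated in advance; it stays defined where the ratio does not.

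The cost is a sentence or two in the Protocol, a short SAP section and a little more analysis work on the same data.

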# **Sensitivity Analysis**

We will perform sensitivity analyses by adopting a range of 'best and worst case' scenarios for resource costs (including actual costs from the three health care systems, or from estimates obtained using charge-to cost ratios), a range of initial depression prevalence, and depression treatment benefit (including considerations of recall bias for self-reported measures). We will also recalculate the incremental cost-effectiveness ratios separately by health care system, so that a range by site can be presented. Multivariate Monte Carlo simulation will be used to obtain 95% confidence intervals for estimates of cost and effectiveness, which will be used to produce a range of incremental cost-effectiveness ratios to determine the robustness of our results. In addition, we will repeat we will repeat our baseline analysis and sensitivity analysis after restricting cost accounting to the payer perspective only.

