# **Protocol Amendments**

# Summary of changes

Affected section	Summary of Revisions Made	Rationale
Study setting: recruitment sites	Duke University ended recruitment June 2015	Insufficient patients were being enrolled from the Duke site
Study setting: recruitment sites	Columbia University Irving Medical Center was added as a recruitment site and [name] assumed the role of Site PI for Columbia, July 2016	
 
To achieve study accrual milestones
 
To increase the diversity of the study population to be inclusive of a greater proportion of ethnically diverse patients.
 

Eligibility	Spanish speakers became eligible for inclusion at the Columbia site, July 2016	There were substantial numbers of Spanish-speaking Hispanic patients at the Columbia site, necessitating their inclusion and broadening generalizability of study findings.
Sponsor/collaborators	[name] assumed the role of Principal Investigator from [name], July 2017.	[name] had assumed other responsibilities
Eligibility	Eligibility criteria were clarified to state that patients were eligible if they had an acute coronary syndrome from 2-12 months, July 2017	This was erroneously entered as 2-6 months on initial clinicaltrials.gov submission.
Outcome measures	Cost of health care utilization was moved from being listed as a co-primary outcome to a secondary outcome on Clinicaltrials.gov, October 2017.	Cost of health care utilization was erroneously listed as a co-primary outcome from the outset. This was verified based upon review of the study protocol and grant submission. The DSMB approved this change, and the change was made while study data was still blinded.

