this randomization group (0.21 \* 0.2 + 0.055 \*0.8 = 0.086). Thus, we anticipate a relative difference in QALYs of 0.031 (0.086 change in the AHA's screen & treat group minus 0.055 in the no screen group). We will have 80% statistical power to detect this difference of 0.031 with a sample size of n=475 participants in each group. We chose to determine sample size based on a pairwise comparison at 80% power in the two-step procedure, as a conservative approach relative to powering based on the F-test (See Statistical Analysis section, below, for further details). Specifically, under the scenario where one group has higher QALY than the other two by an effect size 0.18, the F-test will yield 84% power. Adding in 5% loss to follow-up, we selected an overall sample size of n=500 in each randomization group for an overall sample size of n=1500. Power analyses are typically based on the primary clinical outcome. We selected the QALY as our primary outcome and did not have specific economic hypotheses that required statistically tests. Therefore, we chose to follow this tradition, and do not present power calculations for our incremental cost-effectiveness ratios.

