5.4 Sample Size Determination

The sample size of the trial was determined based on an assumed standard deviation for QALYs of 0.17.5 Additionally, based on a general health-related quality of life outcome in a prior study of management of depression for patients with cancer, we assumed a net improvement in QALYs of 0.155 over 18 months of follow-up for depressed individuals who receive depression treatment in the Screen, Notify and Treat group.6 We assumed a 0.055 gain in QALYs for all patients not directly linked to depression treatment (i.e., those in the No Screen group, the Screen & Notify group and those without elevated depressive symptoms in the Screen, Notify, and Treat group). An important consideration for this trial is that only 20% of patients randomized to the Screen. Notify and Treat group were expected to meet criteria for elevated depressive symptoms and thus, to receive depression treatment. Therefore, assuming an increase in QALYs of 0.21 (0.055 background improvement + net improvement of 0.155) over the 18-month follow-up period for the 20% of patients diagnosed and treated for depression in the Screen, Notify, and Treat group and a 0.055 improvement in QALYs for the 80% of patients in this randomization group without depression, an overall gain in QALYs of 0.086 over the 18 month follow-up period was anticipated in this randomization group (0.21 * 0.2 + 0.055 * 0.8 = 0.086). Thus, we anticipated a difference in QALYs of 0.031 (0.086 change in the Screen. Notify, and Treat group minus 0.055 in the No Screen group or Screen and Notify Group), leading to an expected effect size of 0.18 (= 0.031/0.17). With this effect size, we determined the sample size per group to be 475, which would yield 80% power for a two-sided t-test at 5% level. We chose to determine sample size based on a pairwise comparison at 80% power in the two-step procedure (described above), as a conservative approach relative to powering based on the F-test. Specifically, under the scenario where one group has higher QALY than the other two by an effect size 0.18, the F-test will yield 84% power. Adding in 5% loss to follow-up, we selected an overall sample size of n=500 in each randomization group for an overall sample size of n=1500.

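### The planned cost-effectiveness ratios have no stated joint uncertainty method, and are unstable where the plan's own figures put the QALY difference at or near zero

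*Protocol*

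**What the plan says.** Under Hypothesis 2 in the Protocol's Statistical Methods, cost-effectiveness is expressed as ratios "calculated sequentially using the ratio of the difference in average cost per participant divided by the difference in average QALY gained". Two are set out: Screen, Notify & Treat (below, Treat) against Screen & Notify, then Screen & Notify against No Screen.

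The Protocol's Sensitivity Analysis holds the only statement on sampling uncertainty. A multivariate Monte Carlo simulation is to supply "95% confidence intervals for estimates of cost and effectiveness, which will be used to produce a range of incremental cost-effectiveness ratios", as a check on robustness. On sites it says: "We will also recalculate the incremental cost-effectiveness ratios separately by health care system, so that a range by site can be presented".

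SAP section 8 defines the cost inputs but gives no uncertainty method for the ratio. I found in neither document a statement that cost and QALY are sampled as pairs, a rule for reporting a zero or negative QALY difference, or a threshold for calling a ratio favorable.

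The design assumptions are in Protocol Sample Size and SAP 5.4. For Treat against a control, "we anticipate a relative difference in QALYs of 0.031". For the two control groups: "We assumed a 0.055 gain in QALYs for all participants not receiving treatment (i.e., those in the No Screen group, the Screen & Notify group".

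**The concern.** Cost and QALY come from the same patients and may be correlated, so uncertainty in their ratio depends on their joint distribution. The Protocol sentence passes intervals, not paired draws, to the ratio. If the ends of one marginal interval are divided by the ends of the other, the correlation is lost, the result does not have 95% coverage, and it has no bounds once the QALY interval includes zero.

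The ratio also behaves badly when its denominator is near zero. A tiny change in the QALY difference flips its sign, and a negative ICER can mean either cheaper and better or dearer and worse. This matters for the Screen & Notify versus No Screen ratio, whose denominator the plan itself assumes to be zero, and for the site-level ratios, where chance variation could be read as real differences between health systems.

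**Working it through.** **Inputs from the documents.** SD of QALYs 0.17 (Protocol Sample Size; SAP 5.4). Difference δ = 0.031 for Treat against either control. Gain of 0.055 in each control group. Planned "with a sample size of n=475 participants in each group" after 5% loss from 500 (500 × 0.95 = 475), "which would yield 80% power for a two-sided t-test at 5% level".

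**Inputs not in the documents, assumed here.** Site sizes: 3 or 4 equal sites (Protocol Recruitment says four health systems, Sensitivity Analysis says three). Cost difference USD 500 to 1,000, cost SD USD 10,000 to 20,000, cost–QALY correlation −0.5 to +0.5, threshold USD 50,000 per QALY.

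**1. The plan's own figure.** n = 2(1.96 + 0.8416)² × 0.17² / 0.031² = 473 per arm after rounding up, against 475 stated. Power at 475 is 80.2%. The plan's figure reproduces.

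**2. Treat versus a control.** SE = 0.17 × √(2/475) = 0.0110 and δ/SE = 2.81. The probability that the 95% QALY interval includes zero is 1 − [Φ(2.81 − 1.96) + Φ(−2.81 − 1.96)] = 19.8%. The estimate itself is zero or negative in only Φ(−2.81) = 0.25% of trials.

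**3. Screen & Notify versus No Screen.** The assumed difference is 0.055 − 0.055 = 0. The QALY interval then includes zero in 95% of trials, the sign of the estimate is a coin toss, and the true ratio is undefined. In 200,000 simulated trials with the assumed costs above, the 2.5th percentile of the estimated ICER ran from about −USD 834,000 to −USD 1.9 million across scenarios, and the 97.5th from about USD 851,000 to USD 1.98 million. More simply, a cost difference of USD 1,000 gives an ICER of USD 32,258 at 0.031, USD 1,000,000 at 0.001 and −USD 1,000,000 at −0.001.

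**4. By site, the 475 per arm shared equally among k sites.** SE = 0.17 × √(2k/475); p = Φ(−δ/SE) is one site's chance of an estimate at or below zero; for at least one site it is 1 − (1 − p)^k.

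| Sites | True difference in every site | SE | Site QALY interval includes 0 | p | At least one site ≤ 0 |
|---|---|---|---|---|---|
| 4 | 0.031 | 0.0221 | 71% | 8.0% | 28% |
| 3 | 0.031 | 0.0191 | 63% | 5.2% | 15% |
| 4 | 0 | 0.0221 | 95% | 50% | 94% |
| 3 | 0 | 0.0191 | 95% | 50% | 88% |

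Real sites will not be equal. The Protocol's Summary of changes records that one site stopped recruiting in June 2015: "Insufficient patients were being enrolled from the Duke site". A smaller site has a larger SE and a less stable ratio; a larger site has the reverse.

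**5. What a range from marginal intervals would do.** In the same simulations at δ = 0.031, the corner range (smallest to largest quotient of interval ends) was bounded in 80% of trials. When bounded it covered the true ratio 97.7% to 99.9% of the time, depending on costs and correlation. Fieller limits, which use the joint distribution, covered it 95.0% to 95.1% of the time.

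**6. Why the correlation matters.** With threshold L, net monetary benefit is L × ΔQALY − ΔCost and its SE is √(L²SE_Q² + SE_C² − 2LρSE_Q·SE_C). For L = USD 50,000, ΔCost = USD 1,000 and cost SD USD 10,000, the mean is 50,000 × 0.031 − 1,000 = USD 550. SE_C = 10,000 × √(2/475) = USD 649. The SE of net benefit is USD 1,041, 852 or 606 at ρ = −0.5, 0 or +0.5. Marginal intervals are the same in all three cases.

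**The case against.** The method sentence begins with a multivariate Monte Carlo simulation. A reader might infer that the plan divides the ends of two separate intervals, but neither document says so. Multivariate may well mean joint draws of cost and effect, in which case the correlation is kept and one clarifying sentence settles that part. This stands: the fault is an incomplete specification, not a proven wrong method.

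A reader might also infer that Hypothesis 2 is decided on these ranges. It is not. The Protocol judges it on base-case ICERs; the Monte Carlo range and the site ICERs come under Sensitivity Analysis, the site range is descriptive, and Protocol Sample Size and the SAP section 8 footnote both say no economic hypothesis test was planned. This also stands, and it limits the consequence. It does not remove the need for a valid statement of uncertainty, because the range is meant to show robustness.

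For the pooled Treat comparison, even the corner range is conservative rather than meaningless, and at the design effect the QALY interval excludes zero about 80% of the time. The claim that the plan could not inform on cost-effectiveness at all would go too far.

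Finally, equal gains in the two control groups are a sample-size assumption, not a forecast, and the true difference may not be zero. But the plan offers no other value, and a small difference leaves the ratio nearly as unstable.

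**Conclusion.** The point holds as a gap in specification together with a poor choice of summary. The plan names no interval method for the ICER and does not say that cost and QALY are handled jointly. If marginal intervals are used, the range is not a 95% interval.

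The instability follows from the plan's own QALY inputs: no stable ratio for Screen & Notify versus No Screen, and a QALY interval including zero in about 20% of trials for Treat versus a control at 0.031 with 475 per arm. The site results (71% per site, and 28% for at least one wrong sign) also assume four equal sites and a uniform effect; with three sites they are 63% and 15%. The dollar and coverage figures rest on assumed costs, correlations and threshold, and serve only as illustration.

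The economic outcome is secondary with no planned test. The primary QALY comparison is not affected.

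**What to change.** In Protocol Sensitivity Analysis and SAP section 8:

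- State that uncertainty comes from resampling patients within arm and site, keeping each patient's cost and QALY together, or from joint Monte Carlo draws that preserve their correlation. Say how this combines with the five imputed datasets of SAP 5.3 and 5.6.
- Report incremental cost, incremental QALY and incremental net monetary benefit with 95% intervals, and a cost-effectiveness acceptability curve over a stated range of thresholds.
- Give an ICER only as a point summary, with its quadrant of the cost-effectiveness plane, and only where the QALY difference is clearly non-zero.
- By site, report cost and QALY differences, or net benefit, with intervals in place of ICERs.

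The cost is SAP wording and modest extra programming, with no new data. The price is that no single ICER per site is available to quote.
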